16.1 CYP3A4 inhibitors

Table 16-1: Strong CYP3A4 inhibitors

Substance name	Inhibitor strength
Boceprevir	Strong
Clarithromycin	Strong
Grapefruit juice	Depend on dose: Moderate or strong
Cobicistat	Strong
Conivaptan	Strong
Delavirdine	Strong
Idelalisib	Strong
Indinavir	Strong
Itraconazole	Strong
Ketoconazole	Strong
Lopinavir	Strong
Mibepradil	Strong
Miconazole	Strong
Nefazodone	Strong
Nelfinavir	Strong
Posaconazole	Strong
Ritonavir	Strong
Saquinavir	Strong
Telaprevir	Strong
Telithromycin	Strong
Tipranavir	Strong
Troleandomycin	Strong
Voriconazole	Strong

16.2 CYP3A4 inducers

Table 16-2: Strong CYP3A4 inducers

Substance name	Inducer strength
Phenobarbital	Strong
Avasimibe	Strong
Carbamazepine	Strong
Enzalutamide	Potent
Hypericum (St John's Wort)	Strong
Lumacaftor	Strong
Methylphenobarbital	Potent
Mitotane	Potent
Phenytoin	Strong
Rifampicin	Strong
Rifamycin	Strong


The Statistical Analysis Plan (SAP) is based on the following clinical study protocol (CSP) version:

- Amendment 07 and 08 global amendments forming integrated protocol Version 6.0, dated 28 NOV 2019

2. Study Objectives

Originally, the study includes the following objectives:

Primary objective:

- assess efficacy of two doses of vilaprisan compared to placebo in women with symptomatic endometriosis

Secondary objective:

- evaluate the safety and tolerability of two different doses of vilaprisan in women with symptomatic endometriosis

Exploratory objective:

- explore efficacy and safety in sub-populations (e.g. subjects with endometriosis diagnosed by imaging vs subjects with surgically confirmed endometriosis)

Other objectives:

- evaluate the variability in exposure in relation to the efficacy and safety for vilaprisan in subjects with symptomatic endometriosis
- confirm psychometric properties of the newly developed Patient-Reported Outcomes (PRO) instruments: Endometriosis Symptom Diary (ESD) and Endometriosis Impact Scale (EIS) (will be analyzed and reported separately)
- evaluate biomarkers to investigate the drug (i.e. mode-of-action-related effect and / or safety) and / or the pathomechanism of the disease including assessments of exploratory biomarkers to investigate disease activity

With the implementation of the protocol amendments 07 and 08 no further recruitment is possible. With the data available from subjects recruited before the temporary pause the original study objectives cannot be reached. Safety evaluations including the added safety evaluations of the endometrium, adrenal glands, bone, and skin may add to the understanding of the safety of vilaprisan.

3. Study Design

This is a multicenter, randomized, double-blind, placebo-controlled, parallel-group study.

The study originally includes the following phases: a screening phase, a placebo-controlled dose-finding phase, followed by a drug-free interval encompassing 2 menstrual bleeding episodes, a placebo-controlled extension phase, and a follow-up phase.

Endometriosis symptoms and their impact on subjects' daily life was to be documented throughout the study, i.e. from start of the screening until the follow-up phase.

Statistical Analysis Plan

Protocol No.: **BAY 1002670/ 15792**

Page: 4 of 5:

With the implementation of the protocol amendments 07 and 08, this study design is no longer valid. No subjects will receive further study drug treatment.

Study design valid with the implementation of amendments 07 and 08:

The study was temporarily paused since December 2018. With the implementation of amendments 07 and 08 no further subjects will be recruited and none of the enrolled subjects will receive further study drug treatment. All subjects who were randomized and started vilaprisan before the temporary pause will be asked to have a comprehensive safety evaluation (with particular focus on endometrial, adrenal, and skin safety) performed, which is implemented with this amendment. This also applies to subjects who have discontinued the study before or during the temporary pause, provided they have taken at least one dose of vilaprisan.

4. General Statistical Considerations

4.1 General Principles

The statistical evaluation will be performed by using the software package SAS release 9.2 or higher (SAS Institute Inc., Cary, NC, USA).

All data will be presented in the subject data listing as they are recorded. Generation of listings will be conducted by or under the supervision of the sponsor's study statistician.

Listings will be generated after all safety data has been cleaned, locked and released for analysis.

Apart from listing generation no further statistical analysis or summary table generation will be conducted.

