The cause and the relevance of the skin sarcomas observed in the mouse carcinogenicity study is unclear but based on the high exposure at which these tumors were found, the relevance for humans treated at the intended therapeutic dose is regarded as limited.

Nevertheless, all study participants who took at least one dose of vilaprisan in any of the currently paused clinical studies will also be asked to undergo careful evaluation in order to demonstrate skin safety of repeated intermittent treatment with vilaprisan via a thorough skin examination by a dermatology expert.

Benefit risk assessment

The parameters measured in the context of the endometrial, adrenal and skin monitoring have been aligned with clinical experts and represent a positive benefit risk balance between their ability to detect relevant pathologies and the low procedure related risks associated with them.

These safety measures for subjects participating in the vilaprisan studies intend to ensure that potential tumors or diseases of the uterus, the skin or the adrenal glands are detected. If detected, it is important to understand that these tumors or diseases are not automatically related to the study drug as they can occur in a certain number of women independently of participation in a clinical study and independently of whether vilaprisan was taken as a study drug or not (“background incidence”). These measures can help to detect such findings, probably even at an earlier stage than it would have become apparent otherwise. Furthermore, the safety measures will generate important data allowing to examine whether vilaprisan has a role in the development of such tumors and diseases.

With the implementation of Protocol Amendment no. 7 no new subjects will be enrolled in the study. Since only limited data is available from subjects enrolled before the temporary pause (8 out of the planned 315), no statistical analysis will be performed for this study. Data collected so far from subjects who received placebo treatment will not be analyzed. Therefore, further unnecessary invasive procedures of the safety evaluation in these subjects are not justified for ethical reasons.

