¹¹ Saliva tests should be performed as soon as possible after this visit to allow for a repeat in case of unevaluable results or for review by one of the adrenal experts in case of abnormal results. The two samples should be returned to the study site preferably on the day after collection of the last sample.

¹² Only to be performed if subject did not have these performed with normal result after end of treatment

¹³ Only to be performed if subject did not have this performed with normal or clinically insignificant result after end of treatment, negative pregnancy test is a prerequisite; for subjects with menstrual cycles the endometrial biopsy should be taken between Day 7 to 15 (inclusive) of a menstrual cycle

¹⁴ The ultrasound must be done before the biopsy

¹⁵ Only to be performed in subjects who did not have a post-treatment endometrial biopsy (defined as biopsy taken at the earliest 7 days before last study drug intake) with a normal result. This is defined as diagnosis of safety read and of all 3 individual components of the multiread to be "benign endometrium" in Part II of the evaluation form. In addition, the majority diagnosis needs to be "PAEC no" in Part IV of the evaluation form. Furthermore, an endometrial biopsy may also be triggered by results of ultrasound examination or bleeding data (see Section 9.6.3.1). The biopsy CRF page needs to be completed for all subjects, including cases where according to protocol no biopsy is required.

¹⁶ The blood should be withdrawn under fasting conditions between 6 am and 10 am.

¹⁷ In subjects who take biotin, the last dose of biotin should be at least 72 hours prior to hormone testing.

Subjects who received treatment with placebo prior to the temporary pause will be asked to return the eDiary device. Thereafter, subjects will be deactivated on the tablet computer.

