Progesterone receptor modulator-associated endometrial changes (PAEC) will be assessed and documented in a systematic way (see Section 9.6.3.1.4). The results of the PAEC assessment will only be reported back to the investigators if they trigger the request for a repeat biopsy. Apart from cases where such a repeat biopsy is necessary, no clinical action for an individual subject is required based on the PAEC assessment results. PAEC assessment results are systematically collected for all samples and will be reported in aggregated form at the end of the study. They should therefore not be reported as AE for an individual subject.

A systematic approach of assessment and evaluation will also be applied to EAPP (see Sections 9.4.1.1 and 9.4.1.3), endometrial hyperplasia, endometrial thickening (see Sections 9.6.3.1 and 9.6.3.4), liver function test (Section 9.6.3.9), adrenal monitoring (Section 9.6.3.8), skin monitoring (9.6.3.10), and BMD (9.6.3.2).

9.6.2 **Pregnancies**

Contraception and pregnancy test

An acceptable nonhormonal method of contraception (ie, either male condom, cap, diaphragm or sponge, each in combination with spermicide) has to be used starting at Visit 1 and continued until the end of the study. This is not required if contraception is achieved by a permanent method such as bilateral fallopian tube blockage (including Essure) of the subject or vasectomy of her partner(s). Barrier contraception (eg, condoms with spermicide) will be dispensed as required by the subject.

At the time points shown in the original schedule of procedures (Protocol Amendment no. 3), urine pregnancy tests will be performed at the study site. A pregnancy test must be performed before the start of study drug treatment in each treatment period (by the subject at home), and always before BMD and endometrial biopsy.

Additional tests should be performed at home if the subject is concerned about being pregnant. All home pregnancy tests will be documented in the hand-held device.

A positive urine pregnancy test shall be confirmed at the study site, for example, with serum pregnancy test or transvaginal ultrasound.

If any pregnancy test performed at Visits 1 or 2 (screening) or Visit 3 (randomization) is confirmed positive, the subject will not be included in the treatment period. If a pregnancy test shows a positive result during treatment, the subject must stop study drug treatment and

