9.6.3.1.4 Assessment of endometrial biopsies

Blinding and distribution of biopsy samples will be organized by the central laboratory.

Central assessment of endometrial biopsies will be performed in 2 steps, i.e. safety assessment and multi-reader assessment. In cases where an abnormality, e.g. atypia or malignancy, cannot be ruled out, readers will select the most severe diagnosis.

¹⁸ Normal defined as: Diagnosis of safety read and of all 3 individual components of the multiread needs to be “benign endometrium” in Part II of the evaluation form. In addition, the majority diagnosis needs to be “PAEC no” in Part IV of the evaluation form.

Safety assessment

The safety assessment will be performed by one pathologist who will be blinded regarding treatment group. The results of the safety assessment need to be available in time to document:

- Any relevant pathology that requires further diagnostic or therapeutic measures according to local medical practice
- Absence of clinically relevant endometrial pathology before the subject leaves the study
- A repeat endometrial biopsy will be requested, if sample is inadequate for evaluation in the safety assessment.
- For follow-up of biopsies with abnormalities see Section [9.6.3.1.5](#).

Multi-reader assessment

The multi-reader assessment will be performed by a panel of pathologists who will be blinded regarding treatment group and time point of sample. This assessment will be performed as batch reads when a sufficient number of samples are available.

A majority consensus diagnosis of the multi-reader assessment is derived from the individual diagnoses of the pathologist panel (single-reader diagnoses), according to pre-specified rules. In the absence of a majority consensus, the most severe diagnosis is used. The derived diagnosis resulting from these rules will be used for primary analysis of endometrial biopsy data. The individual diagnoses of each reader will be captured in addition.

Starting with Protocol Amendment no. 7, the majority diagnosis of the multi-reader assessment (Part II of the evaluation form, i.e. the diagnoses benign endometrium, endometrial hyperplasia or malignant neoplasm) will be communicated to the study sites once the majority consensus diagnosis is available.

A repeat endometrial biopsy will be requested, if sample is inadequate for evaluation in the majority multi-reader assessment.

For follow-up of biopsies with abnormalities see Section [9.6.3.1.5](#).

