Besides standard safety criteria (e.g., proliferative/secretory/atrophic endometrium, endometrial hyperplasia, malignant neoplasm) the pathologists will document the presence of PAEC (see Section [9.6.3.1.6](#)). The results of the PAEC assessment will not be reported back to the investigators except if in the last biopsy within the study, PAEC is still present and further biopsy sampling is needed.

The main study evaluation will be based on the majority diagnosis of the multi-reader assessment. An analysis of single-reader diagnoses that is more severe than the majority diagnosis will be provided in the Study Report. Investigators will be informed in addition about a single-reader diagnosis (Part II of the evaluation form) that is more severe than the majority diagnosis (Malignant neoplasm > Endometrial Hyperplasia > Benign endometrium).

While the relevant diagnosis for study purposes is the majority result of the multi-reader assessment, any single reader diagnosis that is more severe than the majority diagnosis should be evaluated by the investigator (or by a gynecologist in case the investigator or sub-investigator is not specifically trained in gynecology) for the necessity of therapeutic

interventions. The minimal diagnostic requirement for those cases is a follow up biopsy. For all follow-up examinations and/or therapeutic interventions all efforts should be taken that these examinations are conducted according to the standards of this protocol (e.g. biopsies should undergo multi-reader assessment) and are documented within the study framework.

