10.1 General considerations

All data will be presented in the subject data listing as they are recorded. Generation of listings will be conducted by or under the supervision of the sponsor's study statistician.

Listings will be generated using Statistical Analysis System (SAS) software after all **safety data** has been cleaned, locked and released for analysis.

Apart from listing generation no further statistical analysis or summary table generation will be conducted. No interim analysis will be conducted.

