6.4 Safety

Safety variables include the following variables:

- Adverse events
- Vital signs
- Endometrial histology (classical histology, diagnosis of PAEC, individual features of PAEC)
- Endometrial thickness and endometrial/ myometrial/ ovarian changes based on ultrasound
- Laboratory parameters
- Findings resulting from liver monitoring
- Findings resulting from adrenal monitoring
- Findings resulting from skin monitoring
- Cervical cytology
- Bone mineral density
- Vaginal bleeding pattern

Safety data will be listed as recorded.

7. Document history and changes in the planned statistical analysis

All derivations of efficacy variables, all statistical analyses and summary statistics were deleted from the protocol with the implementation of the protocol amendment 07 and 08 to reflect that only a few subjects were randomized and/or received study medication.

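### Do the endometrial analyses still promised in protocol 9.6.1.6 and 9.6.3.1.4 require a change to the listings-only plan?

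*SAP*

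**What the plan says.** SAP 4.1 sets the rule: "Apart from listing generation no further statistical analysis or summary table generation will be conducted". Protocol 10.1 carries the same sentence. Both sections also state that all data go into the subject listings as they were recorded.

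Three sentences elsewhere in the protocol were written for a fuller analysis:

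- 9.6.1.6, on PAEC: "PAEC assessment results are systematically collected for all samples and will be reported in aggregated form at the end of the study".
- 9.6.3.1.4, on the majority diagnosis from the pathologist panel: "The derived diagnosis resulting from these rules will be used for primary analysis of endometrial biopsy data".
- 9.6.3.1.4, on disagreement between readers: "An analysis of single-reader diagnoses that is more severe than the majority diagnosis will be provided in the Study Report".

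SAP 6.4 and protocol 10.3.1.3 give the histology item only in general terms: "Endometrial histology (classical histology, diagnosis of PAEC, individual features of PAEC". Neither names the reads that the listing will show.

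**The concern.** Read literally, the protocol promises a pooled PAEC report and two biopsy analyses, while its own statistical section and the SAP exclude any analysis or summary table. Someone writing the study report could ask which text to follow.

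Two features make this look more than cosmetic. First, endometrial safety is one of the stated purposes of the closeout follow-up. Second, 9.6.1.6 uses the pooled PAEC report as part of its reason for not recording PAEC as an adverse event in individual women. If the pooled report is not produced, part of that reason goes.

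There is also a question about the listing. The protocol's definition of a normal post-treatment biopsy is stricter than a benign majority. A listing that showed only the majority could not tell a reader whether that definition had been met.

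**Working it through.** No formula is at issue, so the check sets the texts side by side.

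**1. Is the mismatch real?** Yes. Sections 6, 7.1 to 7.4 and 10.4 of the protocol are marked as no longer valid; 9.6.1.6 and 9.6.3.1.4 are not. Section 9.6.3.1.4 even contains a provision that starts with Amendment 7. The SAP is based on protocol Version 6.0 and the protocol supplied is Version 7.0, but the Amendment 9 change table does not list 9.6.1.6, 9.6.3.1.4 or section 10. The version gap does not explain the mismatch.

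**2. Is there doubt about which text governs?** No. The benefit-risk part of protocol section 3 says that no statistical analysis will be done because only 8 of 315 planned subjects were enrolled, and adds: "Data collected so far from subjects who received placebo treatment will not be analyzed". Section 15.4 records that all analyses and summary statistics were removed from section 10. SAP section 7 says the same.

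**3. How far does each sentence conflict?**

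| Sentence | Against the listings-only rule |
|---|---|
| PAEC in pooled form (9.6.1.6) | Clear conflict: pooling implies a summary |
| Primary analysis on the derived diagnosis (9.6.3.1.4) | Weak conflict: it mainly says which diagnosis is the reference one, and a listing can carry that |
| Analysis of more severe single reads (9.6.3.1.4) | Partial conflict: with at most 8 women, a case description in the report would serve, and that is neither a statistical analysis nor a summary table |

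**4. What will the listing contain?**

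| Item | Recorded? | Listed under SAP 4.1 and protocol 10.1? |
|---|---|---|
| Safety read | Yes (9.6.3.1.4) | Yes |
| Each panel read | Yes, captured for each reader (9.6.3.1.4) | Yes |
| PAEC diagnosis and features | Yes (9.6.3.1.6) | Yes, also named in SAP 6.4 |
| Derived majority diagnosis | Obtained and sent to sites since Amendment 7 | Not stated, and not barred: the rule against deriving variables covers efficacy only (SAP 6.2, protocol 10.3.1.1) |

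The definition of normal in Table 9-1, footnote 15, can therefore be checked. It reads "This is defined as diagnosis of safety read and of all 3 individual components of the multiread to be" benign, together with a panel majority of no PAEC. The safety read and the panel reads are recorded data.

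The derived diagnosis can also be recovered. For an adequate sample there are three readers and three main categories (benign, hyperplasia, malignant). Either at least two readers agree, or all three differ and the stated fallback takes the most severe. This assumes that majority means two of three, because the protocol does not set out its pre-specified rules in full.

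**5. Size.** 8 / 315 = 2.5% of the planned sample. Under 1:1:1 allocation the expected number on vilaprisan is 8 × 2/3 = 5.3. The actual split is not given.

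**6. Would a summary add anything?** A simple count of women with PAEC would need a time point. Biopsies may come from screening (6.2), the end of treatment period 1 or 2 (7.3), closeout (Table 9-1) or repeat sampling (9.6.3.1.6), and 9.6.3.1.6 recognises PAEC that was present before treatment. An undated count in about five women would mix pre-existing and later findings. A listing by subject and biopsy tells the reader more.

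**The case for a change.** The strongest case for acting is that the three sentences are current text, that SAP section 7 says the analyses were deleted although traces remain, and that endometrial safety is the part of this study that still matters. On that view a few sentences would cure the mismatch at almost no cost, and the SAP could name the reads so that nobody has to infer them.

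Part of this stands. The wording in 9.6.1.6, and less sharply in 9.6.3.1.4, was not brought into line with section 10, and the SAP does not say that the derived majority will be printed.

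The argument that the report's endometrial content is undefined does not stand, because the general rule lists everything recorded. Nor does the definition of a normal biopsy call for a special output. It decides whether another biopsy is needed and is not a reporting endpoint. SAP 6.4 describes its other safety items, such as adrenal findings, at the same level of detail.

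The adverse-event rationale loses one support but keeps the others: PAEC is collected systematically for every sample, and no individual clinical action follows from it outside the repeat-biopsy cases. PAEC also remains visible subject by subject in the listings.

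**Conclusion.** The inconsistency is real but clerical, and the plan need not change. One phrase, pooled PAEC reporting, clearly contradicts the listings-only rule. The other two sentences can be met by a listing and a short case description. The governing decision is stated and explained in both documents, so a competent report author would follow it.

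The remaining gap, whether the derived majority diagnosis is displayed, is one that analysts fill sensibly: it is already obtained, and it can be recovered from the listed reads. Biopsies taken after closeout are provided for by the report addendum in protocol 11.3.

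At most 8 women are involved, about 5 of them exposed if allocation was balanced, and no estimate, test or conclusion is planned that could be affected. This conclusion rests on two readings: that the listing rule in protocol 10.1 and SAP 4.1 is applied as written to every recorded read, and that the panel majority means two of three.
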